8.3.6. Electrocardiograms

A standard single 12-lead ECG will be recorded after 10 minutes of supine rest according to the schedule shown in Table 8-1.

Table 8-1 ECG collection plan

Study visit or cycle	Day	Time relevant to dosing
Screening	-28 to -1	n.a.
		Predose ^a
	1	0.5-2 hours postdose
Cycle 1		4-6 hours postdose
	8	Predose ^a
		0.5-2 hours postdose

n.a.: not applicable.

a To be performed prior to blood sampling.

If several ECGs (scheduled and unscheduled) are performed during the screening, the latest results should be recorded and used.

If ECGs are performed at the same time point as blood sampling (safety laboratory tests), ECG readings should be taken prior to sampling.

All ECG readings will be performed locally by the Investigator, or a cardiologist will be consulted if clinically indicated.

Additional ECGs can be performed if clinically indicated.

Abnormal ECG findings

In case of **abnormal** ECG findings (e.g., QTcF prolongation >30 ms compared to baseline, or QTcF interval >500 milliseconds, Torsade de pointes, ventricular tachycardia, ventricular fibrillation, flutter or any other new cardiac abnormality), triplicate ECG readings will be performed. If the abnormal ECG finding is confirmed after triplicate ECG readings, the participant should be referred to a local cardiologist.

Significant QTcF prolongation is defined as an interval >500 milliseconds (ms) or an interval which increases by 60 ms over baseline.

Management of participants with significant QTcF prolongation

If the QTcF prolongation is confirmed by **either** criterion (i.e., QTcF interval >500 ms **or** >60 ms increase from baseline) the following actions will be taken (see also Table 6-1):

- The treatment with xevinapant/matched placebo must be interrupted.
- The participant will be monitored including assessment of electrolytes in plasma (potassium calcium and magnesium), treated appropriately and closely followed (ECGs at least 3 times per week) until resolution to within 30 ms from baseline or QTcF <480ms.
- Stop any concomitant medication known to cause QTc prolongation.
- The participant will be referred to a cardiologist.
- The medical monitor will be consulted prior to administering further xevinapant/matched placebo doses.
- If the QTcF interval does not return to within 30 ms of baseline or <480 ms within 14 days, xevinapant/matched placebo must be permanently discontinued.

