1.1 Synopsis 5.2 Exclusion Criteria	#18 - History of other malignancies: T1a squamous esophageal carcinomas added as an exception.	SCCHN patients with early squamous cell carcinoma of the esophagus (ESCN) are similar in prognosis as patients without ESCN and therefore can be considered eligible for clinical studies as the natural history and treatment does not have the potential to interfere with the safety or efficacy assessment of the investigational drug.	9.0
	#19: Contraindication changed to include both MRI and CT scans	Participants able to undergo either enhanced MRI or enhanced CT can enter the study.	
1.1 Synopsis 5 Study Population 5.5 Strategies for Recruitment and Retention 10.2.1 Sample Size	Assumed screening failure rate changed to 30% with approximately 1000 participants being screened.	Based on the currently observed screening failure rate the numbers have been adjusted.	9.0
1.3 Schedule of Assessments Section 8.3.6 Electrocardiograms	Remove ECG assessment at C4.	Available data do not suggest xevinapant has long-term effects on ECG.	9.0
1.3 Schedule of Assessments 8.3.7 Laboratory Tests 13.2 Cisplatin Administration	Additional renal function monitoring to take place 48 hours (±12 hours) after cisplatin infusion.	Monitoring included to avoid or mitigate renal toxicities.	9.0
4.1 Study Design and Overview 6.3 Measures to Minimize Bias	Introduction of a Firewall Team as an additional oversight committee.	Added to keep the study team blinded at Interim Analysis until a decision is made if the results are sufficient for a regulatory filing.	9.0

Section # and Name	Description of Change	Brief Rationale	Version Implemented

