Qualitative variables will be summarized by frequency counts and percentages. Unless otherwise stated the calculation of proportions will be based on the number of participants of the analysis set of interest. Therefore, counts of missing observations will be included in the denominator and presented as a separate category.

Descriptive statistics by nominal visit or time point, e.g., for laboratory measurements, will include only data from scheduled visits. Unscheduled visits will be included in the derivation of baseline or worst on-treatment values.

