15.3 Clinical Laboratory Evaluation

Clinical laboratory results assessed by central and local laboratory will be graded according to NCI-CTCAE, Version 5.0 (see Appendix 3) and classified as low, normal, and high, or normal/abnormal according to the laboratory normal ranges.

All hematology, blood biochemistry, urinalysis, coagulation, and serology evaluations will be listed per participant for each assessment. Standard International System (SI) units will be used for listing and reporting. For continues laboratory results assessed by the central laboratory, actual value observed and change from baseline summary tables will be provided for each laboratory parameter by visit and treatment arm, together with the maximum on-treatment change. For categorical laboratory results frequency tables showing the number and percentage of participants will be provided for each laboratory parameter by visit and treatment arm.

For statistical and graphical summaries of the safety laboratory tests, values below or above the limit of detection (e.g., '<3' or '>500') are substituted with the lower/upper limit of detection (e.g., '<3' is substituted by 3, '>500' is substituted by 500). In the participant data listings, the values will be shown as collected, e.g., including the < or > sign.

69/104

Abnormalities classified according to NCI-CTCAE will be described using the maximum grade. For those parameters which are graded with two toxicities such as potassium (hypokalemia/hyperkalemia), the toxicities will be summarized separately. Low direction toxicity (e.g., hypokalemia) grades at baseline and post baseline will be set to 0 when the variables are derived for summarizing high direction toxicity (e.g., hyperkalemia), and vice versa.

Shifts from baseline NCI-CTCAE grades to maximum on-treatment NCI-CTCAE grade will be presented by treatment arm for central and local laboratory results. Only scheduled visits will be included in the change from baseline summary table; however, unscheduled visits will be included in maximum post-baseline shift tables, liver function tests summaries, and participant data listings. Abnormal laboratory results will be presented in an additional listing.

In addition, a boxplot will be presented for each laboratory parameter assessed by the central laboratory by treatment arm, showing the distributions of change from baseline at each ontreatment study visit.

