15.5 Other Safety or Tolerability Evaluations

15.5.1 ECG

A standard single 12-lead ECG will be recorded according to the schedule shown in Table 8-1 of the protocol. In case of abnormal ECG findings, triplicate ECG readings will be performed. Abnormal ECG results including heart rate (bpm), PR interval (msec), RR interval (msec), QRS duration (msec), QT interval (msec), QTcF interval (msec) and morphology rhythm, and classification of within normal limits, abnormal not clinically significant, and abnormal clinically significant with a description for abnormal findings will be presented in a participant data listing.

Actual value observed and change from baseline summary table will be provided for each ECG parameter by visit, time point and treatment arm together with the maximum on-treatment increase/decrease. The maximum on-treatment increase/decrease from baseline will be calculated by ECG measurement (heart rate increase/decrease, PR interval increase, RR interval increase, QRS duration increase, QT interval increase and QTcF interval increase). In case of triplicate ECG readings, the mean of the triplicate ECG parameter values will be used for calculations. For delta QTcF the 90% 2-sided CI will be additionally included with a flag if upper bound > 10 msec.

Shifts from baseline to worst post-baseline values will be presented for the ECG overall evaluation. Additionally, the number and percentage of participants with noteworthy on-treatment QTcF values (<= 450 msec, >450 to 480 msec, >480 to 500 msec, >500 msec) at each timepoint, the number and percentage of participants with noteworthy on-treatment QTcF changes from baseline (<=30 msec, >30 to 60 msec; >60 msec) will be provided by treatment arm for each post-baseline timepoint. In addition, for each post-baseline timepoint the number and percentage of participants with any QTcF value > 500 msec and QTcF change from baseline > 60 msec during the ontreatment period will be displayed.

A box plot will be presented for each ECG parameter by treatment arm, showing the distributions of change from baseline at each on-treatment study visit and timepoint.

Only scheduled visits will be included in summary tables and figures. All visits will be included in the participant data listing.

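### SAP 15.5.1 limits ECG tables to scheduled visits, so the maximum on-treatment change and worst post-baseline shift would stop at Day 8, contrary to the SAP's own general rule

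*SAP*

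**What the plan says.** SAP 15.5.1 takes its collection times from the protocol: "A standard single 12-lead ECG will be recorded according to the schedule shown in Table 8-1 of the protocol". That table ("Table 8-1 ECG collection plan", protocol 8.3.6) lists screening, C1D1 (one predose and two postdose tracings) and C1D8 (one predose and one postdose). The schedule of events in protocol Table 1-1 marks the same three visits. The amendment history gives consistent background ("Remove ECG assessment at C4"). Beyond that, protocol 8.3.6 says "Additional ECGs can be performed if clinically indicated", and it requires repeated tracings each week after significant QTcF prolongation.

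SAP 15.5.1 then promises, among other outputs:

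- a by-visit summary of each ECG parameter, accompanied by the maximum on-treatment increase or decrease;
- a shift from baseline to the worst post-baseline category of the overall ECG evaluation;
- QTcF category counts at each timepoint;
- a count, introduced as being for each post-baseline timepoint, of participants "with any QTcF value > 500 msec and QTcF change from baseline > 60 msec during the ontreatment period will be displayed".

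The section ends: "Only scheduled visits will be included in summary tables and figures". All visits go to the listing.

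The general rule in SAP 9 separates two cases. By-visit statistics use scheduled visits, but "Unscheduled visits will be included in the derivation of baseline or worst on-treatment values". SAP 9.13 repeats the distinction: unscheduled assessments stay out of per-timepoint summaries but enter endpoints not tied to a timepoint. For laboratory data, SAP 15.3 states that "unscheduled visits will be included in maximum post-baseline shift tables".

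**The concern.** A maximum or a worst value is meant to summarise the whole period at risk. If only scheduled visits feed it, and the schedule ends in the second week of Cycle 1, the table carries an on-treatment label but describes the first eight days. Platinum is given again in Cycles 2 and 3, and xevinapant or placebo continues to Cycle 6. An ECG taken for cause in those cycles is the kind of tracing most likely to show a prolonged QTcF, and it would be missing from the maximum-change table.

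The matter is descriptive safety reporting. No efficacy endpoint, hypothesis test or participant-level safety action depends on it. It still matters because the protocol presents its ECGs as QTc monitoring and because QTcF above 500 ms and an increase above 60 ms are the protocol's own action thresholds. A reader of the study report would naturally take these tables as whole-treatment evidence.

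**Working it through.** There is no stated figure to reproduce. The check compares the rules and then does the schedule arithmetic.

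**Step 1: timing of the last scheduled ECG.** Cycles last 21 days, so Day 1 of cycle k is study day 1 + 21(k − 1): Days 1, 22, 43, 64, 85 and 106, as in protocol Table 1-1. The last scheduled ECG, C1D8, is Day 8.

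**Step 2: length of the on-treatment period.**
- Dosing is on Days 1–14 of six cycles (protocol 6.1.2.1), so the last planned dose is 106 + 13 = Day 119.
- Check: the end-of-treatment visit 15 days later is Day 134, as Table 1-1 shows.
- SAP 9.5 ends the on-treatment period 30 days after the last dose: 119 + 30 = Day 149.

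**Step 3: coverage.**
- Of the on-treatment period: 8/149 = 5.4%, leaving 149 − 8 = 141 days (94.6%).
- Of the span from first to last planned dose: 8/119 = 6.7%.
- Of planned dosing days: 6 × 14 = 84, and 8/84 = 9.5%.

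These figures measure time. They do not count ECGs or events.

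**Step 4: each output against the general rule.**

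| Output in SAP 15.5.1 | Type | SAP 9 / 9.13 would use | 15.5.1 closing sentence uses | Result |
|---|---|---|---|---|
| By-visit summaries, box plots | by timepoint | scheduled | scheduled | consistent |
| QTcF categories at each timepoint | by timepoint | scheduled | scheduled | consistent |
| Maximum on-treatment increase/decrease | worst value | all on-treatment | scheduled | **contradiction** |
| Shift to worst post-baseline evaluation | worst value | all post-baseline | scheduled | **contradiction** |
| QTcF >500 ms and change >60 ms | mixed wording | unclear | scheduled | ambiguous |

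**Step 5: the ambiguous row.** The sentence opens as a per-timepoint display but then refers to any value during the on-treatment period, which is a whole-period quantity. Its *and* can mean one joint criterion or two separate ones. The joint reading corresponds to the protocol 8.3.6 case in which both criteria are met. The text settles neither question.

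**Step 6: comparison with other safety sections.** SAP 15.3 follows the general rule for laboratory shifts. SAP 15.4 limits vital signs to scheduled visits in the change table only. Vital signs are scheduled at Day 1 of every cycle and at end of treatment, so the restriction costs far less there. The ECG sentence is the broadest of the three and meets the shortest schedule.

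**The case against.** The strongest reply is that the texts can be reconciled. SAP 9 governs how a worst value is derived, and the closing sentence of 15.5.1 governs which visits are tabulated. The SAP does not say that a specific section overrides a general one, so one cannot assert that the table would be programmed the narrow way. This stands as a caution. It does not remove the problem, because the sentence covers every ECG summary table without exception and the two readings give different tables.

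A second reply is that the restriction concerns visits rather than ECGs. C2D1 to C6D1 and end of treatment are scheduled visits, and a clinically indicated tracing done at one of them might be admitted. The SAP does not say so, and 15.5.1 ties its schedule to Table 8-1, so the plain reading excludes it. Triplicates taken at C1D1 or C1D8 may well be included.

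A third reply is that the signal appears elsewhere, and this is largely right. Clinically significant ECG findings are to be reported as adverse events (protocol 9.1.1), and the treatment-emergent tables cover the whole on-treatment period. The legacy AESI row in SAP 15.2.3.4 and Appendix 2 includes confirmed QTcF increases above 30 ms and states no visit restriction. The listing holds all visits. Some AESI sections are redacted, so further QT displays cannot be ruled out. The legacy row, however, pools QTcF with other ECG abnormalities and gives no count at 500 or 60 ms.

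A reader might infer that every QTcF above 500 ms or change above 60 ms after Day 8 is lost from the tables in breach of the general rule. The documents do not support that. The category tables are by timepoint and follow the rule, the 500/60 ms display is only ambiguous, and later events are reported through the routes above.

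**Conclusion.** The contradiction is established for two outputs, the maximum on-treatment change and the worst post-baseline shift. On the plain reading, both stop at Day 8 of a planned 149-day on-treatment period (5.4%), whereas SAP 9 and 9.13 would include later unscheduled ECGs. The 500/60 ms display needs its wording settled but is not shown to break the rule.

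This rests on two assumptions: that an ECG outside Table 8-1 does not count as belonging to a scheduled visit, and that the participant completes six cycles on the planned dates. The number of later ECGs, and of QTcF excursions among them, cannot be known from the documents, so the day fractions must not be read as a share of events missed. The point merits correction before database lock; it does not threaten the trial's main conclusions.

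**What to change.** In SAP 15.5.1:

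- Confine the scheduled-visit sentence to by-visit and by-timepoint summaries and box plots.
- State that all on-treatment ECGs, including unscheduled ones (mean of triplicates where taken), enter the maximum-change and worst-shift outputs.
- Replace the ambiguous display with an any-time on-treatment count of participants with QTcF above 500 ms, with change above 60 ms, and with both.
- Footnote these outputs to say that ECGs after C1D8 are clinically triggered.

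This brings the section into line with SAP 9, 9.13 and 15.3. The cost is SAP wording and a programming flag, since the all-visits listing shows that the data are already planned for reporting. The drawback is that later ECGs are symptom-driven, so the counts may look slightly less favourable and are not a systematic sample of treatment time. The footnote tells the reader so.

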15.5.2 ECOG Performance Status

All ECOG-PS results will be listed. The number and percentage of participants with each score will be presented by treatment arm at baseline and at each scheduled post-baseline visit. In addition shifts from baseline to worst post-baseline scores will be presented.

All visits will be included in the participant data listing.

15.5.3 Transfusions

The number of transfusions received per participant will be presented, together with the type of transfusion by treatment arm. A supporting participant data listing will be provided.

15.5.4 Ear Examination and Audiogram

For clinical ear examination assessment and audiogram the Investigator's interpretation will be presented in a frequency table by visit and treatment arm. A supporting participant data listing will be provided.

[figure not shown]
15.5.5 Dental Examination

[figure not shown]
Dental examination data will be listed at each time point.

[figure not shown]

15.5.6 Nutritional Status

Nutritional status data will be listed at each time point.

16.2.3 Key Baseline Covariates for HRQL Analysis

Key baseline covariates that should be included in all regression models for HRQL analysis are the following:

Randomization stratification factors (from IWRS):

- Primary tumor site: larynx versus other (oropharynx and hypopharynx);
- Lymph node involvement: N0-1 versus N2 versus N3;
- T size: T4 versus other;

Other covariates:

- ECOG-PS: 0 versus ≥ 1 ;
- Age (continuous);
- Gender;
- Baseline HRQL score (for the item/scale in question in the analysis).

Key baseline covariates include stratification factors for randomization.

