6.3. Measures to Minimize Bias: Randomization and Blinding

To ensure that treatment assignment is unbiased and concealed from participants and Investigator staff, randomization will be performed using the following procedure.

All participants will be centrally assigned to randomized study intervention using an IWRS. A web address and a manual for the IWRS will be provided to each site. The Investigator or authorized person will be responsible for activating the IWRS.

During screening or at C1D1 and upon confirmation of eligibility, the participant will be randomized to one of the 2 study arms in a 1:1 ratio. Each medication kit will be identified by a unique medication number. To avoid unintentional unblinding, those numbers will be assigned following a randomized sequence. At the D1 visit of each cycle, the IWRS will assign 2 kit numbers per participant.

Eligible participants will be randomized in a 1:1 ratio to receive xevinapant + CRT (Arm A) or matched placebo + CRT (Arm B). The following stratification factors will be considered for the randomization:

- Region: North America vs Western Europe vs Rest of the World.
- Primary tumor site: larynx vs other.
- Lymph node involvement: N0-1 vs N2 vs N3.
- T size: T4 vs other.

The randomization mechanism will have 2 stages:

- First stage: randomization will be either to "balanced part" (with probability 0.2) or "adaptive part" (with probability 0.8).
- Second stage: randomization will be based on the result of the first stage. If randomization from the first stage is:
 - to the "balanced part": treatment assignment will be in a 1:1 ratio to either xevinapant + CRT (Arm A) or matched placebo + CRT (Arm B), regardless of the stratification factors.
 - to the "adaptive part": a dynamic allocation will be carried out following the methodology proposed by Pocock et al. (Pocock et al. 1975; Lebowitsch et al. 2012). An Overall Imbalance Score (OIS, using the range measure) will be calculated based on levels of individual stratification factors of participants both for the scenario when xevinapant + CRT will be assigned and scenario when placebo will be assigned. Based on the values of OIS for each arm, probabilities for assignment will be derived:
 - If OIS is the same for both arms, then the randomization will be 1:1 to either xevinapant + CRT or placebo + CRT.

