8.2.1 Randomization stratification factors (from IWRS)

The following subgroups are relevant for all endpoints listed in Section 8.2.

Region

- North America
- Western Europe (as defined in Appendix 4) (reference level)
- Rest of the World

Primary tumor site

- Larynx
- Other (Oropharynx and Hypopharynx) (reference level)

Lymph node involvement

- N0-1 (reference level)
- N2
- N3

T size

- T4
- Other (T1, T2, T3) (reference level)

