14.2 Secondary Efficacy Endpoints and Analyses

This section describes the statistical methods for the analysis of the secondary efficacy endpoints. All secondary endpoint analysis will be performed on ITT. Confirmatory testing will only be done for OS. For all other secondary endpoints, no formal statistical hypotheses will be tested.

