16.2.5.2 Primary Health-Related Quality of Life Analysis

The endpoints of the primary HRQoL analysis will be the change from baseline at the end of combination therapy (any measurements until day 74) and at the completion of investigational therapy for EORTC QLQ-C30 subscale scores on GHS and fatigue and EORTC QLQ-HN35 subscale scores on swallowing and pain.

For the analysis of change from baseline until end of combination therapy (any measurements until day 74), HRQoL observations will be excluded after completion of combination therapy (whileon-treatment strategy). For the analysis until completion of the investigational therapy (EOT), observations will be excluded that are obtained in the EFS follow-up (while-not-in EFS followup) and also measurements after start of subsequent therapy (while not treated with subsequent anti-cancer therapy). Change from baseline in the primary PRO-endpoints will be analyzed by means of analysis of covariance (ANCOVA). The ANCOVA model will include the treatment arm, the randomization strata (from IWRS as given in Section 16.2.3) as classification factors and the PRO baseline score as covariate. The average effect of study interventions from randomization until end of combination therapy (any measurements until day 74) or treatment discontinuation or death, whichever comes first, and the average effect of study interventions from randomization until end of treatment or death, whichever comes first, will be compared between interventions using the difference in terms of least-squares means from the ANCOVA model. The difference in least squares (LS) means, corresponding standard error, 2-sided 95% confidence interval, 1-sided p-value for the difference between interventions will be presented without adjustment for multiplicity.

Supplementary analyses will be performed repeating ANCOVA but including the covariates as given in Section 16.2.3 as fixed factors.

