16.2.5.3 Exploratory Health-Related Quality of Life Analysis

Treatment groups will be compared for the time points until end of treatment following the ANCOVA model above for all EORTC QLQ-C30 and HN35 domains in addition to the primary domains above and also for EQ5D-VAS.

The effect sizes including 95% confidence intervals in terms of differences in LS means will be displayed in a Forest plot accordingly.

Unadjusted mean PRO scores will be graphically displayed over time for all EORTC QLQ-C30 and HN35 domains and EQ5D-VAS. Time points with a low number of patients under observation (<10) will be excluded.

Musoro et al (2020) published "Minimally important differences for interpreting European Organisation for Research and Treatment of Cancer Quality of Life Questionnaire Core 30 scores in patients with head and neck cancer" in 2020 that will further guide analysis and interpretation of within and between group comparisons for all scales/items included in EORTC questionnaires.

 \mathbb{CC}

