Appendix 6 – Programming Specifications

Stratified log-rank test:

```
proc lifetest data= ADTTE;
   time AVAL * CNSR(1,2,3,4);
   strata T N / group= TRTPN test= (logrank) trend;
   ods output TrendTests= logrank;
run;

CNSR ≠ 0 if censored, 0 otherwise
AVAL = EFS time in months
Randomization stratification factors: T = Tumor size, N = Lymph node involvement
TRTPN = planned treatment
```

Cox-Regression:

```
proc phreq data= ADTTE;
  class REGION(ref='Western Europe') SITE(ref='Other') N(ref='N0-1')
        T(ref='Other') TRTP (ref='Placebo') /param=ref;
 model AVAL*CNSR(1,2,3,4) = TRTP REGION SITE N T / rl ties = discrete;
 hazardratio 'treatment' TRTP/ diff=ref;
 hazardratio 'region' REGION / diff=ref;
 hazardratio 'tumor site' SITE / diff=ref;
 hazardratio 'lymph node' N / diff=ref;
 hazardratio 'T size' T / diff=ref;
 ods output HazardRatios= HR;
run;
CNSR \neq 0 if censored, 0 otherwise
AVAL = EFS time in months
Randomization stratification factors:
REGION = Region, SITE = Tumor Site, T = Tumor size, N = Lymph node involvement
TRTP = planned treatment
```

[figure not shown]
Kaplan-Meier Estimates:

```
proc lifetest data=ADTTE timelist=9,12,18,24,30,36 outsurv=surv reduceout;
  time AVAL * CNSR(1,2,3,4);
  strata TRTPN;
  ods output Quartiles=quar;
  ods output ProductLimitEstimates=est;
run;

[figure not shown]
CNSR ≠ 0 if censored, 0 otherwise
AVAL = EFS time in months
TRTPN = planned treatment
```

[figure not shown]
Logistic regression model:

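### Region, one of the four randomization factors, is missing from the HRQL covariate list in SAP 16.2.3, so no HRQL ANCOVA adjusts for it

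*SAP*

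**What the plan says.** Protocol 6.3 allocates dynamically on four factors: primary tumour site, lymph node involvement, T size and "Region: North America vs Western Europe vs Rest of the World". SAP 8.2.1, whose heading begins "8.2.1 Randomization stratification factors (from IWRS", lists the same four, and SAP 10.2 names all four again when it defines incorrect stratification as a deviation.

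SAP 16.2.3 sets the covariates for all HRQL regression models. Under the same label as 8.2.1 it lists site, N and T. Its other covariates are ECOG-PS, age, gender and the baseline score. Region appears in neither group, yet the section ends: "Key baseline covariates include stratification factors for randomization".

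The HRQL models all depend on that list:

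- The primary ANCOVA (SAP 16.2.5.2) enters "the randomization strata (from IWRS as given in Section 16.2.3) as classification factors", together with arm and baseline score.
- The supplementary ANCOVA (same section) adds the remaining 16.2.3 covariates.
- The exploratory comparisons (SAP 16.2.5.3) are made "following the ANCOVA model above for all EORTC QLQ-C30 and HN35 domains" and for the EQ5D-VAS.

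The Cox model for EFS, which OS follows, does contain region: the code in SAP Appendix 6 has "TRTP REGION SITE N T" on the right-hand side.

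**The concern.** The list and the sentence that closes it do not match if the stratification factors are those of Protocol 6.3 and SAP 8.2.1. Because every HRQL model points back to this list, the gap carries through to the reported least-squares mean differences, confidence intervals and one-sided p-values for global health, fatigue, swallowing and pain, and to the exploratory domains.

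When allocation has balanced on a factor, the treatment estimate already benefits from that balance. If the factor is prognostic and left out of the model, its variance stays in the residual, and the model-based standard error is larger than the true one. Intervals are then too wide and tests too conservative. What is at stake is the calibration of the HRQL intervals and an unambiguous model, not the validity of the comparison.

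**Working it through.** **Which factors count.** The only figure in the documents that bears on the list is in the history of protocol amendment 5 (Protocol 13.10.1.1.5), which says the four randomization factors make 36 strata. Region (3 levels) × site (2) × N (3) × T (2) = 36, which reproduces it. The three factors in SAP 16.2.3 give 2 × 3 × 2 = 12. The stated figure needs region.

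**Effect on the reported interval.** Let R² be the share of residual variance that region explains after baseline score, site, N and T. The documents give no value, so 0%, 2%, 5% and 10% are assumed. With region balanced between arms,

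reported SE without region ÷ reported SE with region = 1/√(1 − R²),

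which is 1.000, 1.010, 1.026 and 1.054.

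**Effect on size and coverage.** These depend on how well the allocation balances region, so they were simulated.

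- From the documents: 700 participants randomized 1:1; probability 0.2 of a plain 1:1 assignment; otherwise a range-based imbalance score over the four factors, with probability 0.8 for the arm giving less imbalance.
- Assumed: region 15/45/40%, larynx 30%, N0-1/N2/N3 35/55/10%, T4 45%, no treatment effect, and either complete data or 30% of scores missing at random.
- Model: ANCOVA on arm, site, N, T and baseline score, fitted without and with region, in 242,500 simulated trials. Monte Carlo error of a 2.5% size is √(0.025 × 0.975/242,500) ≈ 0.03 percentage points.

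Results with region omitted:

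| Assumed R² | CI wider by | Size, complete data | Coverage, complete data | Size, 30% missing | Coverage, 30% missing |
|---|---|---|---|---|---|
| 0% | 0% | 2.5% | 95.0% | 2.5% | 95.1% |
| 2% | 1.0% | 2.4% | 95.3% | 2.4% | 95.2% |
| 5% | 2.6% | 2.2% | 95.6% | 2.3% | 95.5% |
| 10% | 5.4% | 2.0% | 96.1% | 2.1% | 95.8% |

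With region in the model, size is 2.5% and coverage 95.0–95.1% in every case.

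**Where the conservatism comes from.** At R² = 10% with complete data, the reported SE is 0.0756 without region and 0.0718 with it. The true SE is 0.0718 without and 0.0716 with. Omitting region therefore hardly changes how variable the estimate is; it overstates that variability by 0.0756/0.0718 = 1.053. As a hand check, Φ(−1.96 × 1.053) = Φ(−2.064) ≈ 0.0195, in line with the simulated 2.0%.

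Missing scores loosen the balance. With 30% missing, adding region lowers the true SE by 0%, 0.3%, 0.8% and 1.8% across the four R² values, and the distortion of size and coverage shrinks.

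**Cross-check.** A separate simulation of 4,000 trials, with slightly different N and T prevalences, gave the same width ratios (1.010, 1.026, 1.054) and 96.3% coverage at R² = 10% with complete data. Its Monte Carlo error for coverage is about √(0.95 × 0.05/4,000) ≈ 0.34 points, so it agrees with 96.1%.

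**The case against.** The strongest reply is that the model as written is clear and breaks no commitment. The closing sentence of 16.2.3 does not say that all factors are included. The later sections point to one list, and a programmer following it would fit site, N and T. Protocol 10.4.3.9 leaves the HRQL analysis to the SAP, and the protocol promises adjustment for the randomization factors only for time-to-event and binary endpoints. Using a subset has a precedent here, since the log-rank tests stratify on T and N alone. Parts of SAP 16.2 are blacked out, so a reason may exist that cannot be seen. The size of the effect rests entirely on assumed values of R².

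Much of this stands. No protocol commitment is broken, and SAP section 7, which records departures from the protocol, had no duty to mention region. The effect is conditional and small.

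The precedent does not carry over. The log-rank tests dropped factors to avoid very small strata (SAP 14.1.1), and they dropped site as well as region, whereas 16.2.3 keeps site. Sparse strata are not a difficulty for an ANCOVA with the factors as main effects. That is the natural reading of classification factors, although no ANCOVA code is visible to confirm it. The 16.2.3 list therefore matches neither the log-rank set nor the Cox set, and it shows no redaction mark. If the omission was deliberate, the label and the closing sentence still need correcting.

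**Conclusion.** The concern holds. SAP 16.2.3 presents three of the four randomization factors as the stratification factors, and no HRQL ANCOVA as specified adjusts for region. The consequence is conservatism only: reported intervals 1.0% to 5.4% wider if region explains 2% to 10% of residual variance, and no effect if it explains none. Those shares, the factor prevalences and the missing-data rate are assumptions; the direction and the width formula are not sensitive to the prevalences.

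The treatment estimate is not biased and type I error is not inflated. Among the secondary endpoints, SAP 14.2 states that "Confirmatory testing will only be done for OS", so no confirmatory conclusion is affected. This is a low-priority correction, worth making because it is almost free and removes an ambiguity before the data are unblinded.

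**What to change.** Add region (three levels, from IWRS) to the stratification factors in SAP 16.2.3. The cross-references then bring it into the primary, supplementary and exploratory HRQL ANCOVAs without further edits. The cost is one line of text and 2 degrees of freedom per model, and the variable is already used in the Cox model. If region was left out on purpose, say so in 16.2.3 with the reason, and correct the label and closing sentence.
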